#### 6.4 STUDY INTERVENTION COMPLIANCE

The following mechanisms will be employed to determine protocol and medication adherence and measure outcomes:

1. An electronic peak flow meter/e-diary device will be used to measure peak expiratory flows (PEF). The device will serve to obtain PEF and will function as a general adherence check (date and time are electronically recorded). Electronic measurements will be transmitted to a central platform and a compliance report will be reviewed with the participants. PrecISE coordinators will provide positive feedback to participants who demonstrate good adherence, and ongoing encouragement when warranted.
2. The PrecISE network will leverage the e-diary platform from Propeller Health (or other provider) to administer a daily question for self-report of intervention compliance. Qualtrics e-diaries have been developed as a backup to the e-diaries provided by Propeller Health. In addition, adherence with the e-diary symptom questions for use in the CompEx serves as a proxy for study procedure adherence in general. A financial compensation structure is planned to promote e-diary adherence, which will in turn promote intervention compliance. Recognizing that self-report may not be fully adequate in assessing intervention adherence, we will use the following procedures/measures to assess adherence as appropriate for each intervention (see appendices): counts of returned pills or capsules for oral formulations, counts of returned packets for powder formulations and counts of in-clinic injections.
3. Participants who take fewer than 60% of doses (active or placebo) required in a 16-week treatment period will be considered in violation of the protocol for that treatment period. The treatment period will be excluded from the per protocol analysis population (see Section 9.4).

#### 6.5 CONCOMITANT THERAPY

Concomitant medications will be reviewed at each study visit. Participants who are receiving immune-modulating therapies for diseases other than asthma will not be permitted to enroll. Participants who are taking biological agents for asthma will be permitted to enroll in the study and will be asked to continue their current biologic throughout the study. Intervention-specific lists of excluded medications are included in Appendices I-V. Table 2 shows the required washout time prior to Screen Visit and visits with spirometry, BDR or methacholine. These withholds may also be used for home spirometry.

**Table 2**

	Washout prior to Screen Visit and visits with Spirometry, BDR or methacholine
Inhaled beta-adrenergic agonists (intermediate-acting, e.g., albuterol, terbutaline, metaproterenol, pirbuterol, bitolterol)	≥ 6 hours
Inhaled long-acting beta-agonists (e.g., Salmeterol/formoterol)	≥ 24 hrs
Taken twice daily	≥ 36 hrs
Taken once daily	
Inhaled anticholinergics	Short-acting: ≥6 hours
Long acting taken twice daily	Long acting BID: ≥24 hours
Long acting taken once daily	Long acting QD: ≥36 hours
Short-acting theophylline (e.g., Slophyllin tablets)	≥ 12 hours
Long-acting theophylline (e.g., Theo-Dur, Slo-bid, Theo24, Uniphyll)	≥ 24 hours
Leukotriene modifiers (Singulair, Accolate, Zflo)	≥ 24 hours
Methylxanthine-containing foods or beverages (e.g., coffee, tea) or medications	≥ 4 hours

Chronic daily or intermittent use of the following medications is allowed (some exclusions may apply for specific interventions – see appendices):

- oral contraceptives and other hormonal forms of contraceptives (e.g., DepoProvera-7, Norplant-7)
- estrogen / progesterone replacement therapy for post-menopausal women
- vitamins and calcium supplements
- any nasal inhaled corticosteroid used at a stable dose throughout the entire study
- acetaminophen
- non-steroidal anti-inflammatory medications (e.g., aspirin, naproxen, ibuprofen, Cox-2 inhibitors)
- thyroid replacement medications
- lipid-lowering medication
- stable dose medical therapy for well-controlled hypertension and well-controlled diabetes, except those meds specifically excluded due to specific intervention exclusions
- medium and low potency topical cutaneous steroids
- nasal saline spray
- topical eye preparations for allergic eye symptoms (e.g. antihistamines, NSAIDs, or antiallergic compounds)
- diuretics and specific antihypertensives (e.g. calcium channel blockers, clonidine, etc.)
- acyclovir
- oral and topical antihistamines
- pseudoephedrine and oxymetazoline and other decongestants
- antibiotics for acne
- non-macrolide antibiotics
- macrolide antibiotics (both chronic and acute use)

- stool softeners and bulk laxatives
- H2 blockers and proton pump inhibitors for GERD
- Imitrex for migraines
- Propecia (finasteride)
- SSRI class antidepressants
- non-SSRI antidepressants
- migraine analgesics (e.g., butalbital)
- antianxiety agents
- ACE inhibitors
- Librax
- CNS stimulants/appetite suppressants

Chronic use of the following medications is not allowed:

- Methotrexate
- Mycophenolate (CellCept®)
- Azathioprine (Imuran®)
- Immune-modulating therapies for diseases other than asthma

---

#### 6.5.1 CONTROLLER MEDICATION

Participants must be taking an additional asthma controller/biologic (defined in Tables 1B and 1C in Section 5.1). Study sites provide controller medication from our supplier to participants beginning at the Screening Visit and at every subsequent visit while the participant is in the study. If a participant prefers to continue the controller medication, they regularly use rather than switch to the controller medication provided by the study, they will be allowed to do so. This information will be documented.

Participants will be encouraged to continue on the provided controller medication for the duration of the trial. If a subject decides to switch controller medication during the trial, this may be allowed, but the cost will not be covered by the trial. Participants will be encouraged to wait until the end of their current 4-month treatment period before changing medications. See Section 6.5.4 for more information on allowed changes in controller medication during the trial.

---

#### 6.5.2 RESCUE MEDICINE

Study sites provide inhaled rescue medication from our supplier to participants beginning at the Screening Visit and at every subsequent visit while the participant is in the study. Participants may use their personal rescue medication as needed as prescribed by their treating physician if they prefer it to the study supplied rescue medication.

- Rescue medications may include: albuterol, levalbuterol, ipratropium and albuterol/Ipratropium. Participants may not use ICS/LABA combination drugs for rescue – i.e. no SMART therapy.
- The use of rescue medications is allowable at any time during the study.
- The study will record the use of rescue medications.

---

### 6.5.3 EPISODES OF WORSENING ASTHMA/EXACERBATIONS

An asthma exacerbation in PrecISE is defined as a worsening of asthma requiring the use of a systemic corticosteroid (at least 3 days of treatment) to prevent a serious outcome. This definition is consistent with recommendations from the NIH Outcomes Workshop. Events meeting one or more of the following criteria will be recorded as asthma exacerbations during the study:

- All worsening asthma events in which systemic corticosteroids were initiated to prevent a serious outcome, including use of systemic corticosteroids in association with any form of healthcare provider encounter
- All asthma-specific emergency department or urgent care visits that involved treatment with systemic corticosteroids (defined as evaluation and treatment for <24 hours in an ED or urgent care center)
- All asthma-specific hospitalizations that involved treatment with systemic corticosteroids (defined as admission to an inpatient facility and/or evaluation and treatment in a healthcare facility for ≥24 hours) (also reported as a serious adverse event)
- All asthma-specific intensive care unit admissions or intubations (also reported as a serious adverse event)
- All asthma-related deaths (also reported as a serious adverse event)

For the purposes of this study, a course of oral systemic corticosteroids (OCS) is defined as any increase of at least 20 mg prednisone or double the daily maintenance dose for a minimum of 3 days. Note that a single depo-injectable dose of corticosteroids or oral dexamethasone will be considered equivalent to a 3-day course of OCS. If the maintenance dose is <5 mg, an increase must be both a doubling of that dose and at least a 5 mg increase (e.g., 2.5 mg would need to increase to at least 7.5 mg to count as a course).

The recommended course of OCS for treatment of an asthma exacerbation that occurs during the study is prednisone 60 mg x 3 days, then tapering by 10 mg each day (60-60-60-50-40-30-20-10-0). If the patient is receiving OCS on a daily basis, the taper ends at that dose. A patient receiving a course of OCS that differs from this recommendation will still be considered as having had an exacerbation, provided one of the defining criteria for an asthma exacerbation listed above is met.

Two courses of systemic corticosteroids must be separated by at least two weeks to count as two exacerbations. The two-week clock starts when the corticosteroid course for the first exacerbation ends.

Exacerbations may result in treatment discontinuation and re-randomization (see Section 7.1) or withdrawal from the study (see Section 7.2).

If no asthma symptoms are present when a course of OCS is started during the study, the OCS use should be reported as a concomitant medication, but the event would not qualify as an asthma exacerbation. For example, if an adult participant starts an OCS course because a family member developed a viral respiratory infection, this OCS course would not be considered a steroid course for asthma, but it would be recorded as a concomitant medication.

Acceptable documentation to support an exacerbation, in order of preference, is as follows:

- Discharge summaries from a hospital, emergency room, or an urgent care facility indicating that a subject was hospitalized/treated with systemic corticosteroids for an asthma exacerbation

- Signed and dated notes from a referring physician, including information regarding diagnosis and treatment of an exacerbation with systemic steroids
- Evidence of prescriptions provided by the participant for systemic corticosteroids used during an exacerbation
- A documented conversation that is recorded in a timely manner between the investigator/nurse or nurse practitioner and a subject who is already on an OCS action plan, detailing the diagnosis and treatment of an asthma exacerbation.
- A documented conversation between the treating/referral physician, health care provider, or nurse/nurse practitioner certifying that a participant was treated for an exacerbation with corticosteroids at their clinic or under their supervision. The dates (month/year) of the exacerbations and verbal confirmation that appropriate prescriptions were provided is necessary. This option should be used only if reasonable attempts to procure participant records have been unsuccessful.

Participants may receive treatment for asthma exacerbations during the study outside of the PrecISE study clinics. We recognize that participants may live some distance from a study site; may wish to have exacerbations managed by their usual provider; may be at work, traveling, or away from home when the exacerbation occurs; and/or may have health insurance that precludes treatment at the PrecISE study site or affiliated hospital. The ethical management of asthma exacerbations in study participants requires that 1) we are prepared to help participants manage these exacerbations, 2) we work to ensure the safety of participants when they seek assistance for an exacerbation, and 3) we work collegially with other health care providers who may be called upon to treat a PrecISE participant.

An informational pamphlet will be provided to each study participant that they can give to a provider in the event of an asthma exacerbation. This pamphlet will inform the provider of: a) the general nature of the PrecISE study, b) the types of interventions in the study, and c) contact information for the study sites.

---

#### 6.5.4 MAJOR CHANGES IN THERAPY

The PrecISE study has special challenges, as participants have severe and/or exacerbation prone asthma not adequately controlled on high-dose ICS plus additional therapy such as a LABA, LAMA, oral CSs, or all three, they may already be on a biologic for their asthma due to disease severity, and they may be in the study for as long as 40 months. As a result, some participants may have their treatment changed while in the study. The number of participants in whom this occurs is difficult to predict, but as more treatments, especially biologics, for severe asthma become available, it is likely to increase.

A major change is:

- the addition, dose adjustment (see below) or discontinuation of an oral corticosteroid for a period of time greater than that specified under treatment of exacerbations (Section 6.5.3) with the intention of continuing such therapy.
- the addition, dose adjustment, or period adjustment of a parenteral corticosteroid administered during the study;
- the addition, dose adjustment, or discontinuation of an additional asthma controller (note that changes within a class of therapy that do not change the dose of that type of therapy are not major changes)
- the addition, dose adjustment, or discontinuation of a biologic therapy believed to affect asthma,
- the addition, dose adjustment, or discontinuation of a beta blocker,

- the addition or discontinuation of azithromycin to a participant's baseline (chronic) regimen for the treatment of asthma.

A major change in asthma therapy typically occurs due to worsening (or dramatic improvement of) asthma, or a perception of worsening asthma by a treating physician, or the availability of a new therapy the treating physician wants to prescribe in the absence of a change in the participant's overall status. Such a change generally occurs outside the period of an asthma exacerbation.

A 5 mg/d change in prednisone (or equivalent) therapy for patients on chronic therapy, outside the strict definition of treatment for an asthma exacerbation in Section 6.5.3, is considered a major change in therapy. Additionally, since the maximum dose of oral prednisone allowed for entry into the study is 10 mg, an increase in oral prednisone therapy to greater than 10 mg daily, outside the strict definition of treatment for an asthma exacerbation in Section 6.5.3, is considered a major change in therapy.

The addition, dose modification, or discontinuation of any immune-modulating therapy, thought to potentially affect asthma pathobiology, for non-asthmatic disease will also be considered a major change in therapy. These treatment changes make it difficult to assess the specific effect of the asthma intervention.

It is expressly noted that a change within a class of therapy that does not change the total dose of that type of therapy is not considered a major change. For example, the patient's insurer may decide to cover one brand of combination ICS/LABA therapy, and the patient may then want or need to switch from the brand he/she is currently using. As another example, a patient may change (for insurance reasons) from one anti-IL-5 biologic to another. These are not considered major changes, whereas a change from one biologic to another for purposes of achieving increased therapeutic efficacy would be considered a major change.

A major change in therapy can occur during a treatment period (test treatment or placebo) or a washout period. In most asthma studies with an intervention lasting up to 12 months, major therapy changes (e.g., addition of a biologic) are not permitted. Consistent with this practice, major changes in therapy will be discouraged during the 4-month treatment periods in PrecISE.

If a participant has a major change in therapy during a treatment period, he/she will discontinue their current assigned treatment, and then discontinue the study. The following guidelines apply:

- Changes that require removal of a therapy, or a decreased dose of therapy, should include the reason for the removal (e.g., adverse event from the medication).
- Likewise, changes that require a new medication for asthma control (e.g., introduction of an anti-IL-5 directed biologic) should include the reason for the addition. When feasible, it is recommended that such changes be done at the end of, rather than in the middle of, an intervention. However, patient safety is paramount in such additions of therapy, and the PrecISE study will not override the judgment of the treating physician.
- Following discontinuation from the study due to a major change in therapy, the participant has the option of re-entering the study as a new participant. Inclusion criteria will be re-assessed to see if the patient still meets the criteria for uncontrolled severe asthma after the change in therapy. The patient will undergo the usual screening and run-in process and additional specimens will be collected. The participant's biomarker profile will be reassessed to determine randomization probabilities. The participant will not receive any interventions already received when previously enrolled.

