- f. Two sequential AST or ALT elevations >3 times the upper limit of normal with at least one total bilirubin value  $\geq$ 2 times the upper limit of normal.
- g. Two sequential AST or ALT elevations >3 times the upper limit of normal accompanied by symptoms consistent with hepatic injury, per the judgment of the center investigator.

- h. Two sequential AST or ALT elevations >5 times the upper limit of normal, regardless of total bilirubin or accompanying symptoms.
- i. Two sequential decreases in eGFR < 54 mL/min/1.73 m^2 and baseline eGFR was >60 mL/min/1.73 m^2 OR eGFR < 50 mL/min/1.73 m^2 and baseline eGFR was 54-60 mL/min/1.73 m^2
- 5. Any safety issue that has required or will require (per the investigator's judgment) interruption to treatment for >28 days.
- 6. Any event (i.e. asthma exacerbation, asthma treatment, or any other medical condition) requiring 21 or more contiguous days of prednisone above the participant's usual baseline dose.

Specific interventions may have additional safety criteria for discontinuing treatment (see appendices).

A participant will be discontinued from treatment if, during an exacerbation, he/she

- Is admitted to an ICU and requires non-invasive positive pressure ventilation or
- Experiences three exacerbations during a treatment period.

If, following treatment discontinuation for any of the criteria listed above, participants are deemed eligible (by safety criteria) to continue in the study, they will enter the 8-week (or longer) washout period preceding the next intervention. Entry into the washout period will begin at least 7 days after completing treatment of the exacerbation with oral or parenteral corticosteroids.

Participants who respond to treatment with systemic corticosteroids or who receive a single IM injection of steroid at the beginning of an exacerbation will not be discontinued from treatment, unless this is their 3rd exacerbation within the same treatment period, in which case, the above treatment discontinuation criteria apply.

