3.5.4 Major Change in Therapy

A major change in therapy is defined in Section 6.5.4 of the protocol. If a participant has a major change in therapy during a treatment period, they will discontinue their current assigned treatment and then discontinue the study. Any assessments collected after the major change in therapy will not be included in the efficacy analyses.

4. Randomization

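### Protocol 6.5.4 and 7.1.1 give incompatible outcomes for a participant given a steroid injection to treat an exacerbation

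*Protocol*

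**What the plan says.** Protocol 6.5.4 lists what counts as a major change in therapy. One bullet reads "the addition, dose adjustment, or period adjustment of a parenteral corticosteroid administered during the study". The bullet for oral corticosteroids is narrower and applies only "for a period of time greater than that specified under treatment of exacerbations (Section 6.5.3) with the intention of continuing such therapy". A later paragraph in 6.5.4 adds "an increase in oral prednisone therapy to greater than 10 mg daily, outside the strict definition of treatment for an asthma exacerbation", so it too sets exacerbation treatment aside.

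A participant with a major change during a treatment period is to "discontinue their current assigned treatment, and then discontinue the study". Section 7.2 item 8 repeats a major change as a reason to leave the study at any point. SAP 3.5.4 adds: "Any assessments collected after the major change in therapy will not be included in the efficacy analyses".

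Protocol 7.1.1 deals with exacerbations during treatment. Participants "who receive a single IM injection of steroid at the beginning of an exacerbation will not be discontinued from treatment", unless this is their third exacerbation in the same period. It also sets the start of washout at a minimum interval after exacerbation treatment has finished, and it names both the oral and the parenteral route. Section 6.5.3, which defines exacerbations, states that "a single depo-injectable dose of corticosteroids or oral dexamethasone will be considered equivalent to a 3-day course of OCS".

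**The concern.** An injected steroid is a foreseeable way to treat an exacerbation in this population. Section 6.5.3 also expects that some exacerbations will be treated outside the study clinics, where the site does not choose the route. Two operative rules then apply to one event, and they lead to different places.

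The choice matters for the analysis as well as for conduct:

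- It decides whether the end-of-period value can enter the efficacy analysis.
- It decides whether the intercurrent event is recorded as an exacerbation or as a major change in therapy. SAP Table 2 lists these separately.
- If the participant is removed before period 2 starts, SAP section 5 does not count that participant towards the required sample size.

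The event is a worsening of asthma. If an intervention alters exacerbations, removals under the stricter reading could differ between active and placebo periods. SAP 7.4.2 sends both informative and non-informative missingness to the same MMRM, so the primary analysis has no separate protection against this.

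**Working it through.** No power or error-rate calculation applies. The check sets the rules side by side and follows one event through them.

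**Step 1. Does 6.5.4 except exacerbation treatment?** Compare its steroid provisions.

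| Provision in 6.5.4 | Refers to 6.5.3? | Duration or intent condition? |
|---|---|---|
| Oral corticosteroid bullet | Yes | Yes, both |
| 5 mg/d change in chronic prednisone (or equivalent) | Yes | No |
| Oral prednisone above 10 mg daily | Yes | No |
| Parenteral corticosteroid bullet | No | No |

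Only the parenteral bullet has no exception. Its first trigger, addition, is unqualified.

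**Step 2. Follow the event through each section.**

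| Event in a treatment period | Under 7.1.1 | Under the literal 6.5.4 bullet and 7.2 item 8 |
|---|---|---|
| First or second exacerbation, one IM injection at onset | Stays on treatment and in the study | Stops treatment and leaves the study |
| Third exacerbation in the period, treated by injection | Stops treatment; if eligible on safety grounds, goes to washout and the next intervention | Stops treatment and leaves the study |

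In the first row the outcomes are incompatible. In the second row both rules stop treatment, and the difference is whether the participant remains in the study.

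**Step 3. Is parenteral treatment expected in participants who remain?** Yes. The washout provision in 7.1.1 covers participants who are about to receive a further intervention, and it mentions parenteral exacerbation treatment. If every parenteral addition ended participation, that mention would have nothing to apply to.

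**Step 4. Follow the data.** SAP 3.5.1 gives four on-treatment visits, X.2 to X.5, with X.5 as the endpoint visit.

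- Injection between X.2 and X.3: under 6.5.4 and SAP 3.5.4, X.2 is kept, and X.3, X.4 and X.5 are excluded or never collected. That is 3 of 4 visits, including the endpoint. Under 7.1.1 all four can count.
- Injection before X.2: under 6.5.4 all four are lost. No usable post-baseline value remains for that period, which puts mITT membership in doubt, because SAP 7.1 requires at least one for each primary endpoint.
- Injection in period 1: under 6.5.4 the period 2 half of the matched pair is not collected either.

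**Step 5. Does any other text settle it?** Section 6.5.4 remarks that major changes *generally* fall outside an exacerbation. That describes what usually happens and exempts nothing. Section 6.5.3 refers exacerbations to 7.1 and 7.2, but 7.2 item 8 leads straight back to 6.5.4.

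**Step 6. Size.** Neither document gives a rate of parenteral steroid use or an expected exacerbation rate. The number of periods affected cannot be derived from them.

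**The case against.** The best defence is that the specific text governs the general. Section 7.1.1 names this exact case, 6.5.3 treats a depot dose as an ordinary exacerbation course, and 6.5.4 is framed around changes of regimen. Its mention of a period adjustment suggests recurring parenteral treatment. On that view the bullet was never meant to reach a single injection in an exacerbation. This is a fair account of what the authors may have intended. It does not remove the conflict: no sentence gives 7.1.1 precedence, the exception written for oral steroid is missing here, and a site that follows 6.5.4 literally is following the protocol.

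Other parts of the defence stand and limit the point:

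- **Loss of all later periods.** A reader might infer that removal is final. It need not be. Section 6.5.4 allows re-entry as a new participant, although only after renewed screening and run-in and without interventions already received.
- **Loss of the whole period.** SAP 3.5.4 excludes only assessments after the change. Earlier visits remain available to the MMRM.
- **Sites have already diverged.** The documents report no divergent handling, and the Manual of Procedures, which might address it, is not among them.
- **A second contradiction on oral steroid.** Section 7.1.1 item 6 stops treatment for an event "requiring 21 or more contiguous days of prednisone above the" participant's usual baseline, including for a non-asthma condition, while 6.5.4 makes oral prednisone above 10 mg daily a major change. These can be read cumulatively: item 6 stops treatment, and 7.2 item 8 separately stops participation. The triggers also differ, since 10 mg daily for 21 days in someone not on oral steroid meets item 6 but does not exceed the 10 mg threshold. Washout under 7.1.1 is conditional on eligibility to continue. How the two interact is unclear, but they do not contradict each other.

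**Conclusion.** The contradiction is in the text and rests on no numerical assumption. For parenteral steroid given as treatment of an exacerbation, the protocol both keeps and removes the participant, and the efficacy data after the event are both used and excluded. The explicit exception in 7.1.1 covers a single IM injection at the start of an exacerbation. Its companion wording, on participants who respond to systemic corticosteroids, would also reach other parenteral use.

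The effect per affected participant can be large (up to all four on-treatment visits of that period and, unless the participant re-enters, the remaining periods). The number affected is unknown. A reader might put in assumed rates:

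- With 1 to 2 exacerbations per year, 1 − exp(−r × 16/52) gives 0.265 to 0.460 of 16-week periods with at least one.
- If 5% to 20% of those involve parenteral steroid, 0.265 × 0.05 = 0.013 and 0.460 × 0.20 = 0.092, or 1.3% to 9.2% of periods.
- The planned study discontinuation of 0.02 per 4 weeks gives 1 − 0.98^4 = 0.078 per 16 weeks.

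It would be tempting to conclude that the conflict could roughly double attrition. The documents do not support that. Both input ranges are assumptions, and the upper end needs the highest value of each and every site applying the literal bullet. If all sites follow 7.1.1 for these events, the bullet adds no removals.

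The point is worth correcting because it concerns a removal rule that also decides which data are analysed.

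**What to change.** Reconcile Protocol 6.5.3, 6.5.4, 7.1.1 and 7.2 item 8 so that one stated outcome applies to parenteral corticosteroid given as treatment of a 6.5.3 exacerbation. Either the parenteral bullet or the 7.1.1 text has to change. Which rule is right is for the sponsor's medical team. SAP 3.5.4 should then follow that rule and say whether such an event is classed as an exacerbation or as a major change in therapy for Table 2 and section 7.4.2.

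The protocol is dated 27 September 2024, and SAP 3.5.2 expects the last on-treatment visit in December 2024, so a change in conduct may reach few remaining periods. The SAP should therefore also state how injections already recorded are classified, decided without knowledge of treatment assignment.

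As a secondary clarification, state how 7.1.1 item 6 and the 6.5.4 sentence on prednisone above 10 mg daily work together when raised prednisone is given for a non-asthma condition.

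The cost is about one sentence of protocol text for the main point and one for the clarification, a matching line in the SAP and a memo to sites. No new visits or data are needed.
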